6.1.2. Definitions and Derivations

Unscheduled visits

Unscheduled visits will not be included in the summary tables but will be included in the listings.

Variables

Baseline is defined as last value prior to first dose of IMP.

Change from baseline will be calculated as follows:

• Change from baseline = post-baseline assessment value – baseline assessment value

Duration [days] will be calculated as follows:

• Duration [days] = last observation date – first observation date + 1

Time from first immunization to first reaction will be calculated as follows:

Time from first immunization to first reaction [days] = first reaction date – prime immunization date + 1

Time from first reaction to last reaction will be calculated as follows:

Time from first to last reaction [days] = last reaction date – first reaction date + 1

Days since last immunization will be calculated as follows:

Days since last immunization = onset date of AE – date of last immunization + 1

For conversion of days to months or years the following rules will be applied:

• 1 month = 30.25 days

• 1 year = 365.25 days

Study Day and Treatment Day are defined as follows:

- · Study day:
- o If study date < date of first dosing, then study day = study date date of first dosing
- o If study date >= date of first dosing, then study day = study date date of first dosing + 1

Fold increase will be calculated as follows:

Fold increase = post-dose value / baseline value

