6.4.1. Solicited local reactions

Definition

Solicited local reactions at the injection site consist of pain, tenderness, erythema/redness or induration/swelling. They are assessed by the subject in a diary and by the investigator at specific time points stated in the protocol.

Local reactions will be graded using criteria based on the guidance given in US Food and Drug Administration (FDA) Guidance for Industry 'Toxicity Grading Scale for Healthy Adult and Adolescent Volunteers Enrolled in Preventive Vaccine Clinical Trials' for 'Local Reaction to Injectable Products'. The grading of local reactions to injectable product is detailed in section 8.2.9 of the protocol. The grades are Grade 0 (Absent), Grade 1 (Mild), Grade 2 (Moderate), Grade 3 (Severe) and Grade 4 (Potentially life threatening).

The solicited local reactions will be evaluated for the following time intervals:

- Prime immunization up to day 7 (inclusive) after prime immunization
- Boost immunization up to day 7 (inclusive) after boost immunization
- Both intervals combined

The intervals will start with the date and time of the immunization.

Clarification: The interval 'prime immunization up to day 7 after prime immunization' includes study day 1 to study day 8. This applies to the other intervals accordingly.

Analysis

Local reactions with missing time and occurring on the day of prime immunization will be assigned to all intervals starting with the prime immunization. Local reactions with missing time and occurring on the day of the boost immunization will be assigned to all intervals including the boost immunization. Local reactions with missing date will be assigned to each of the respective intervals if it cannot be ruled out, that it belongs to the time interval.

The following analyses will be done for local reactions assessed by the subject, for local reactions assessed by the investigator and for both combined:

Differing from protocol section 9.4.2, the number and percentage of subjects reporting at least one local reaction in each time interval will be summarized for any local reaction and by worst grade.

The denominator of the percentages will be the number of subjects with any information on local reactions in the diary available in the respective time interval.

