The number and percentage of subjects reporting at least one local reaction will be summarized by local reaction type (pain, tenderness, erythema/redness and induration/swelling) and by worst grade for each time interval. The denominator of the percentages will be the number of subjects with any information on local reactions in the diary available in the respective time interval.

The following analyses will be done for local reactions assessed by subjects:

Statistical Analysis Plan Version: Final 3.0

Time after prime and after boost from

EudraCT No: 2020-003267-26

- · first dose to first local reaction,
- first dose to first local reaction with grade >=3,
- · first local reaction to last local reaction and
- first local reaction with grade >= 3 to last local reaction with grade >= 3

will be summarized descriptively overall and by local reaction term.

The same variables will be described for any reaction (local or systemic).

Moreover, the frequency of subjects with solicited local reactions and any solicited reactions within 7 days after each dose per day and the frequency of subjects with solicited local reactions within 7 days after each dose by term per day will be analyzed.

The compliance with the diary from each immunization up to 7 days after each immunization will be presented. Therefore, a table giving the number and percentage of subjects with any information on local reactions in the diary (overall and by local reaction term) available per day will be given.

The compliance with the diary based on any information on any reaction (local or systemic) will also be given.

All local reactions from the study will be listed. Additionally, all days with information on local reactions in the diary will be listed.

Local reactions assessed by subject will be presented graphically using a bar plot.

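### Reaction-onset time is defined only from the prime dose but is also summarized after boost; as written, the post-boost onset summaries do not give time since boost

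*SAP*

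**What the plan says.** SAP 6.1.2 contains one derivation for the onset of a reaction: "Time from first immunization to first reaction [days] = first reaction date – prime immunization date + 1". SAP 6.4.1 introduces the timing summaries with "Time after prime and after boost from" and then names the first dose as the starting point, both for onset of any grade and for severe onset; the latter item reads "first dose to first local reaction with grade >=3". The summaries are requested overall, by reaction term, and for local and systemic reactions together. SAP 6.4.2 applies the same analysis to systemic reactions.

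Elsewhere SAP 6.4.1 works per immunization. On the analysis intervals it says "The intervals will start with the date and time of the immunization". The second of them is "Boost immunization up to day 7 (inclusive) after boost immunization". Daily frequencies are counted "within 7 days after each dose per day". For day numbering it clarifies: "The interval 'prime immunization up to day 7 after prime immunization' includes study day 1 to study day 8", and says that the other intervals follow the same pattern. An interval combining both periods is also defined.

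The only derivation in SAP 6.1.2 that counts from a later immunization, days since last immunization, is written for AE onset. SAP 7.1 (Appendix 1), which lists changes from the protocol, does not touch the point.

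**The concern.** A post-boost onset table is meant to show how soon after the boost a reaction begins, next to the same figure for the prime dose. The written derivation cannot give that figure, because the boost date does not appear in it. SAP 6.4.1 does not correct it: by naming the first dose, it repeats the prime origin. A programmer who follows both sections has written support for a result that is not time since boost, and a quality check against the SAP could confirm it.

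At stake are the post-boost onset summaries for any grade and Grade ≥3, for local, systemic and any reaction. They would not be comparable with the post-prime summaries beside them. The formula also leaves open which reaction counts as the first, and the two possible meanings fail in different ways.

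**Working it through.** **Inputs**

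- Prime immunization: study day 1 (study-day rule, SAP 6.1.2).
- Boost: study day B = 20 to 24, nominally 22 (Visit 4, Day 22±2; Protocol 1.3, Table 3 footnote h).
- Days from an immunization to the first reaction in its interval: k = 0 to 7 (SAP 6.4.1).

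**Reproducing the plan's own day count.** After prime, the reaction falls on study day 1 + k. The formula gives (1 + k) − 1 + 1 = k + 1, which is 1 to 8. This matches the SAP's clarification, so the formula is right for the post-prime summaries.

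**Reading 1: first reaction means the first in the boost interval.** The reaction falls on study day B + k.

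- As written (prime origin): (B + k) − 1 + 1 = B + k.
- Boost origin: (B + k) − B + 1 = k + 1.
- Shift: (B + k) − (k + 1) = B − 1.

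| Boost on study day | As written, k = 0 to 7 | From boost date | Shift (days) |
|---|---|---|---|
| 20 | 20 to 27 | 1 to 8 | +19 |
| 22 | 22 to 29 | 1 to 8 | +21 |
| 24 | 24 to 31 | 1 to 8 | +23 |

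Overall, 20 to 31 days instead of 1 to 8. Because the shift depends on B, variation in the boost visit also enters the spread. As an assumed illustration, take 12 subjects who all react one day after boost: the correct value is 2 for everyone, SD 0. As written, if all are boosted on Day 22, everyone has 23 and the SD is still 0. With six boosted on Day 20 and six on Day 24, the values are 21 and 25, mean 23, SD = 2 × √(12/11) = 2.09. That split is deliberately extreme. Boost days spread evenly over the five window days would give a population SD of √2 = 1.41.

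**Reading 2: first reaction means the subject's first in the trial.** A subject who reacted j days after prime (j = 0 to 7) has the value j + 1 in the post-prime summary, and the same value again in the post-boost summary. A subject who first reacted after boost has B + k, again 20 to 31. The post-boost row would mix the two.

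**One subject, three results.** Reaction two days after prime, boost on Day 22, reaction one day after boost:

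- From the boost date: 1 + 1 = 2 days.
- Reading 1: 22 + 1 = 23 days.
- Reading 2: 2 + 1 = 3 days, the post-prime value repeated.

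**What does not move.** Reaction rates by interval and worst grade, post-prime onset, per-day frequencies and listed dates do not use this formula for the post-boost period.

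**The case against.** The strongest reply is that this is a gap in wording that any competent programmer would close. The formula is correct for the variable that it names; only a counterpart for the boost is missing. The lead-in to the summaries, the start of the intervals and the per-dose daily frequencies all point to the immunization that opens each interval. Table shells and programming specifications are not among the documents, so nothing shows that the prime origin was programmed. Post-boost timing is also visible in the daily frequencies, all reactions are listed, and SAP 6.1.1 plans quality control. A median of 22 days in a 7-day window would hardly pass unnoticed.

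Most of this stands, and it keeps the point minor. Two parts do not. First, the per-dose reading has to override two written statements that name the prime dose, one in 6.1.2 and one in 6.4.1. Second, the claim that an error would show itself holds only on reading 1. On reading 2 the repeated values lie between 1 and 8 and look plausible.

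A reader might infer that 20 to 31 days is the only literal result. It is not: it requires first reaction to be taken within the boost interval while the origin stays at prime. A reader might also take the SD of about 2 as an expected distortion; it rests on an assumed extreme split of boost days and has no basis in the documents.

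**Conclusion.** The definition is inconsistent and wrong as written for the post-boost summaries; the point is minor. On reading 1 the values are 20 to 31 days instead of 1 to 8, a shift of +19 to +23 days (nominal +21). On reading 2 the post-boost value repeats the post-prime onset for subjects who reacted after prime. With a boost-date origin and the first reaction in the boost interval, both errors disappear.

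The range assumes that the boost is given within Day 22±2; a boost outside that window would widen it. Both results are conditional on the text being followed literally.

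Two stronger conclusions are tempting and not supported. One is that the primary reactogenicity results are in doubt: the rates by interval and worst grade do not use onset time, and no hypothesis is tested. The other is that the reported onset tables are in fact wrong: the documents show an inconsistent instruction, not what was programmed.

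**What to change.** Four small changes:

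1. In SAP 6.1.2, define *time from immunization to first reaction = first reaction date in the interval − date of the immunization that starts that interval + 1*. Apply it separately to the prime and boost intervals, and likewise to the first Grade ≥3 reaction.
2. In SAP 6.4.1, replace the reference to the first dose with *the immunization that starts the interval*. SAP 6.4.2 then follows by its cross-reference.
3. For the combined interval, state which origin is used, or that onset is not summarized there.
4. As a programming check, require values of 1 to 8 in the separate prime and boost intervals only. In the combined interval, counted from prime, a first reaction after boost would properly exceed 8. The range check does not detect reading 2; the words *in the interval* in the definition are what exclude it.

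The cost is one definition, one wording change and one added sentence in the SAP, plus a simple check on any tables already produced. No new data are needed.

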6.1.3. Missing data

As a general rule, missing data will not be substituted (i.e., missing data will not be replaced but will be handled as "missing" in the statistical evaluation), with the following exception for summary analyses:

Clinical safety laboratory variables given as '<xx' will be evaluated as 0.5 * xx in the summary tables. In the listings they will be displayed as "<xx" or similar.

6.2. Subject Dispositions

For the SCR, a listing of subjects having failed screening will be presented.

Subject disposition will be listed with date of informed consent, date of screening, date of immunization and date of study completion/discontinuation.

The number and percentage of subjects in the analysis sets will be summarized by group (i.e. by cohort) and cohort-total for the subjects in the SAF.

For the SAF, number and percentage of subjects having prematurely discontinued the study with a summary of the primary reason (e.g., adverse events, death, withdrawal by subject, lost to follow-up), of subjects who completed the end of treatment phase (merged from End of Trial variable and End of Treatment variable (each subject has only one data entry)) and who completed the follow-up phase will be presented by group (i.e. by cohort) and cohort-total.

Subjects having prematurely discontinued will be listed with date and reason for premature discontinuation.

Subjects in the SCR but excluded from SAF, subjects in SAF but excluded from SAFB/ IMM/ IMMPP will be listed with reason for exclusion.

6.3. Baseline Characteristics

6.3.1. Demographics

Demographic and baseline variables will be summarized for subjects in the SAF. Age (calculated as Age[years] + age_month [months]/12), weight [kg], height [cm], and body mass index (BMI) (kg/m²) will be summarized as continuous data by cohort and cohort-total.

Sex (male vs female), ethnicity (Hispanic or Latino, Not Hispanic or Latino, Not reported, Unknown) and race (White, Black or African American, Asian, American Indian or Alaska Native, Native Hawaiian or Other Pacific Islander, Not reported, Unknown, Other) will be summarized as categorical data by cohort and cohort-total.

A listing of demography will be provided.

6.3.2. Concomitant Medication

Prior and concomitant medications will be defined using start and stop dates recorded, relative to the first and last dose of study medication. Any medication taken before 28 days prior to the start date of IMP will not be classified as prior or concomitant medication. A prior medication will be defined as any therapy taken 28 days prior up to (but not including) the start date of IMP.

A concomitant medication will be defined as any medication either

- Taken prior up to (but not including) the start date of IMP and
 - o ongoing at the first vaccination
 - o or with a missing end date
- or with a start date on or after the first vaccination up to 28 days after the last vaccination.

If a medication cannot be clearly assigned to prior medication due to missing dates, it will be evaluated as concomitant medication.

Medications will be coded using the WHO Global (Drug Insight) September 1, 2020 B3 standard drug codes resulting in Anatomical-Therapeutic-Chemical (ATC) codes indicating therapeutic classification.

Listings of prior and concomitant medications will be provided.

6.3.3. Medical History

Medical history data will be coded using the Version Medical Dictionary for Regulatory Activities (MedDRA®) coding system 23.1 including specific terms for COVID-19.

A listing of medical history data will be provided.

6.4. Primary Analyses

Hereinafter, the primary analyses for Part A are described.

The primary endpoints are solicited local reactions at the injection site, solicited systemic reactions and the proportion of subjects with at least 1 unsolicited treatment emergent adverse event (TEAE).

Clarification: Only local and systemic reactions assessed by subject will be analysed as primary endpoint. As additional analyses, the local and systemic reactions assessed by the investigator will also be included in tables displaying "worst possible grade" for data completeness.

All primary analyses will be performed using the SAF and analyses of adverse events will possibly be repeated using the SAFB.

All primary analysis endpoints will be summarized by group (i.e. by cohort) and all cohorts combined (cohort-total).

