# 6.6.1 Dose limiting toxicity

During the time of enrollment into a given dose escalation cohort in Part A, if any of the following events occur, it will be considered an individual dose limiting toxicity and further dosing in that cohort will be stopped:

- Anaphylactic reaction considered related.
- Generalized urticaria considered related.
- Four trial subjects in that cohort with any severe unsolicited local event, if considered related and not manageable with simple measures (e.g., cooling, analgesia, nonsteroidal anti-inflammatory drugs [NSAIDs]).
- AEs within 7 days of vaccination assessed by the investigator to be potentially lifethreatening (Grade 4) and that are possibly related, or for which there is no alternative, plausible, attributable cause.
- Any systemic SAE within 7 days of vaccination that is assessed by the investigator as possibly related, or for which there is no alternative, plausible, attributable cause.
- Any fever >40.0°C (>104.0°F) within 7 days of vaccination considered related and confirmed by an investigator or medically qualified person.
- Two trial subjects (at any dose level) with the same or similar severe (Grade 3 or higher) AE or reactogenicity (including clinically significant laboratory abnormalities) within 7 days of vaccination, considered related, or for which there is no alternative, plausible, attributable cause (for severity grading of AEs see Section 10.3.1.7).

Approval from the SRC will be required prior to any further dosing in the affected cohort. The SRC may call for the opening of a lower dose level cohort.

The same events will prompt IMP discontinuation for individual subjects as described in Section 6.6.4. Tasks connected to the discontinuation of IMP are described in Section 7.1.

The above guidance regulates how potential dose limiting toxicities may influence the decisions to further enroll trial subjects in any cohort. These decisions are taken by the SRC based on the 48 h safety data from the first 6 subjects of each cohort (see Section 4.1). Due to the staggered sentinel dosing design, subjects will have been followed for 4 d for the sentinel subjects when this SRC decision is made.

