5.1. Analysis Sets

Screened Set (SCR)

The screened set is defined as all subjects who signed informed consent.

Safety Set (SAF)

The safety set is defined as all subjects who received at least one dose of Investigational Medicinal Product (IMP).

Safety Boost Set (SAFB)

The safety boost set is defined as all subjects who received two doses of IMP (prime and boost immunization).

Immunogenicity set (IMM)

The immunogenicity set is defined as all subjects who received at least one dose of IMP and have at least one post-baseline functional antibody titer immunogenicity assessment.

Immunogenicity per-protocol set (IMMPP)

The immunogenicity per-protocol set is defined as all subjects included in the immunogenicity set that have no major protocol deviations as determined by the clinician.

Note: In all analysis sets, subjects will be assigned to the dose cohort according to the actual dose they received ("as treated").

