6.4.2. Solicited systemic reactions

Definition

Solicited systemic reactions consist of nausea, vomiting, diarrhea, headache, fatigue, myalgia, arthralgia, chills, loss of appetite, malaise, or fever. They are assessed by the subject in a diary and by the investigator at specific time points stated in the protocol.

Solicited systemic reactions will be graded based on the guidance given in US Food and Drug Administration (FDA) Guidance for Industry 'Toxicity Grading Scale for Healthy Adult and Adolescent Volunteers Enrolled in Preventive Vaccine Clinical Trials'. The grades are Grade 0 (Absent), Grade 1 (Mild), Grade 2 (Moderate), Grade 3 (Severe) and Grade 4 (Potentially life threatening). Fever is graded as Mild (38.0-38.4°C), Moderate (38.5-38.9°C), Severe (39.0-40.0°C and Potentially life threatening (>40.0°C).

The solicited systemic reactions will be evaluated for the following time intervals:

- Prime immunization up to day 7 (inclusive) after prime immunization
- Boost immunization up to day 7 (inclusive) after boost immunization
- Both intervals combined

The intervals will start with the date and time of the immunization.

Clarification: The interval 'prime immunization up to day 7 after prime immunization' includes study day 1 to study day 8. This applies to the other intervals accordingly.

Analysis

Solicited systemic reactions will be analyzed in the same way as solicited local reactions (see Section 6.4.1 of the SAP).

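### Boost-interval solicited reactions cover only boosted subjects and no matching prime table is planned, so reading across the two intervals can understate an increase at the boost

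*SAP*

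**What the plan says.** SAP 6.4 puts every primary analysis on the safety set, that is, everyone with at least one dose: "All primary analyses will be performed using the SAF and analyses of adverse events will possibly be repeated using the SAFB". SAP 6.1.1 is firmer about that repeat, stating that some adverse event analyses will be rerun in the boosted set if the two sets differ. Neither section extends the repeat to solicited reactions.

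SAP 6.4.1 fixes the denominator for local reactions as "the number of subjects with any information on local reactions in the diary available in the respective time interval". It defines a prime interval, a boost interval and the two combined, and adds: "The intervals will start with the date and time of the immunization". SAP 6.4.2 carries this over: "Solicited systemic reactions will be analyzed in the same way as solicited local reactions".

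On who receives the boost, Protocol 6.6.1 lists dose limiting toxicities. These include Grade 4 events, related fever above 40.0°C, and the same or similar severe event or reactogenicity in two subjects, each within 7 days of vaccination. It then says: "The same events will prompt IMP discontinuation for individual subjects as described in Section 6.6.4". Protocol 7.1 lets subjects who tolerated their first vaccination receive the second while the safety committee reviews. Protocol 10.3.1.11 ends further vaccination in a subject with confirmed, related fever above 40.0°C.

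**The concern.** An unboosted subject has no boost interval, because the interval starts at the immunization. The prime percentages therefore describe all primed subjects with a diary, and the boost percentages only those who went on. The variable being tabulated, reactogenicity after the prime dose, can help decide who enters the second interval. If so, the boosted subjects are selected for having tolerated the first dose.

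The primary objective (SAP 1.1) is to describe tolerability after prime and boost. A reader will naturally compare the two intervals to see whether reactions worsen at the second dose. Selection of this kind biases that comparison towards no increase.

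**Working it through.** **The plan's own figure.** SAP 4 gives 85.8% as the chance of seeing a 15% event at least once in 12 subjects: 1 − 0.85^12 = 0.8578, which agrees. With 11, 10 or 9 boosted subjects the same formula gives 83.3%, 80.3% or 76.8%.

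**Inputs**
- Cohort size 12 (SAP 1.2 and 4).
- d, subjects not boosted because of prime reactions. The documents give no rate; Protocol 7.1 calls discontinuation rare. Assumed range 0 to 3 of 12.
- R, subjects with the reaction after the prime dose. Assumed.
- Diaries are assumed complete. Worst case: all d unboosted subjects are prime reactors, so R ≥ d.

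**Formula.** The prime rate in all primed subjects is R/12. In the boosted subjects it is (R − d)/(12 − d). The understatement of the prime-to-boost change is the difference:

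R/12 − (R − d)/(12 − d) = d(12 − R) / [12(12 − d)]

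This is largest at R = d, where it equals d/12.

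| d | R = 3 | R = 6 | R = 9 | Bound d/12 |
|---|---|---|---|---|
| 0 | 0 | 0 | 0 | 0 |
| 1 | 6.8 | 4.5 | 2.3 | 8.3 |
| 2 | 15.0 | 10.0 | 5.0 | 16.7 |
| 3 | 25.0 | 16.7 | 8.3 | 25.0 |

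(percentage points)

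**Examples with assumed counts, d = 2**
- R = 2, then 2 of 10 at boost. Planned tables: 2/12 = 16.7%, then 20%, a change of +3.3. Same subjects: 0/10 = 0%, then 20%, a change of +20.
- R = 6, then 5 of 10 at boost. Planned: 50% then 50%, no change. Same subjects: 4/10 = 40% then 50%, +10.
- R = 6, then 8 of 10 at boost. Planned: +30. Same subjects: +40. The increase stays visible.
- R = 6, but only one of the two unboosted subjects was a prime reactor. Prime rate 6/12 = 50% overall and 5/10 = 50% in the boosted: no distortion.

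**Combined cohorts.** The effect is smaller in a total if few subjects are affected. With 84 subjects (seven cohorts of 12), R = 42 and d = 4: 42/84 − 38/80 = 50.0% − 47.5% = 2.5 points. With d = 8: 50.0% − 34/76 = 5.3 points.

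**Adverse events behave differently.** SAP 6.1.1 makes the analysis-set N the default denominator, and SAP 6.4.3 states no other. A boost event in 5 of 10 boosted subjects would thus appear as 5/12 = 41.7%. The repeat in the boosted set addresses this.

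**The case against.** The strongest counter-case is that nothing is concealed and no comparison is planned. The objective is descriptive, no testing is foreseen (SAP 6.1), and the safety-set prime tables keep every prime reactor. SAP 6.2 gives analysis-set counts by cohort and lists subjects outside the boosted set with the reason. SAP 6.4.1 adds a combined interval and listings of reactions and diary days. With 12 subjects per cohort a reader can find the one or two unboosted subjects. The numbers are also too small for firm conclusions: exact 95% intervals are about 2–48% for 2/12, 3–56% for 2/10 and 0–31% for 0/10.

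Much of this stands, and it limits the point to a descriptive improvement. But the listings only let a reader rebuild the comparison by hand, and the combined interval mixes one-dose with two-dose subjects. Neither gives prime and boost rates in the same people.

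The selection mechanism may also rarely operate. A single Grade 3 solicited reaction is not by itself a listed toxicity. The documents' clearest example of boosts withheld for tolerability, in the related candidate BNT162b1 (Protocol 4.3), concerned whole dose levels. In a cohort like that the boosted set would be empty and the extra table would add nothing within the cohort. It would still matter in the cohort total, which would include that cohort at prime and omit it at boost. A deleted status table in the amendment log (Protocol 10.10.8, as of 30 November 2020) shows 12 primed and 10 boosted at 30 µg in younger adults. It gives no reasons, and boosting may have been unfinished. It indicates a scale and does not show selection.

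A reader might go further and infer that the plan hides any increase at the boost. It does not: the distortion is bounded and larger increases remain visible. Nor do the documents support saying that the effect is worst at the highest doses of this vaccine, or that adverse events share the problem.

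**Conclusion.** The point holds for solicited local and systemic reactions. Prime and boost percentages rest on different subjects, the protocol's own rules can make that difference depend on prime reactogenicity, and no prime table in the boosted subjects is planned. The source is the interval-specific diary denominator in SAP 6.4.1 and 6.4.2, combined with a boosted-set repeat limited to adverse events. The sentence in SAP 6.4 shows only that limit.

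The size is at most d/12 per cohort. At R = 6 it is 4.5 to 16.7 points for d = 1 to 3. It is zero when all are boosted, and zero in expectation when missing the boost is unrelated to prime reactions. The values of d and R are assumptions, and complete diaries are assumed throughout. The boosted-only denominator is itself appropriate, since an unboosted subject cannot react to a boost. The primary tables remain valid descriptions of each interval; the addition is modest but worth making.

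**What to change.** Keep the safety-set tables as primary. Add to SAP 6.4.1 and 6.4.2:

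*Where SAF and SAFB differ in a cohort, prime-interval solicited reactions (any, by type, by worst grade) are also presented for SAFB subjects beside the boost interval, with the number not boosted. Any descriptive statement comparing boost with prime uses the SAFB columns.*

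For adverse events, align SAP 6.4, which leaves the boosted-set repeat open, with SAP 6.1.1, which commits to it for some analyses when the sets differ.

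The cost is a few extra descriptive tables on a set already defined, needed only for cohorts with unboosted subjects and for their combined totals. Part A vaccination was complete by 12 March 2021 (Protocol 4.1) and the trial is open-label (SAP 1.2), so the sponsor can already tell which cohorts are affected.
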